Screening at baseline: 1. Height and weight to calculate BMI. 2. Screening interview- Age, number of cigarettes per day for past year, use other nicotine or tobacco products, current smoking cessation or weight loss treatment/medication. 3. Medical conditions and medications screening tool will be used to screen for recent medical, substance-related, or psychiatric hospitalizations and any medical conditions or medications that warrant exclusion for safety (determined by PI and study Medical Monitor). 4. Participants will complete questionnaires to assess for symptoms of disordered eating (Eating Disorders Assessment (EDA), severe depression or suicidality (total score  $\geq 20$  or question 9 score  $\geq 1$  on the Patient Health Questionnaire 9-item depression index (PHQ-9), reviewed by clinician), or substance or alcohol use disorders (CAGE-AID score  $\geq 2$ , reflecting past 6 months). 5. Salivary cotinine and/or exhaled carbon monoxide (CO) to confirm smoking status.

Feasibility. In order to quantify feasibility of recruitment and enrollment during pilot testing the number of participants screened and enrolled will be documented per month during periods of active recruitment. The proportion of enrolled participants completing planned assessment sessions will be calculated.

Acceptability. Treatment attendance- Attendance at all counseling sessions will be recorded. Percentage of participants completing each treatment session will be calculated to examine treatment-specific retention rates. Participant Feedback- Participants will complete brief assessments at weeks 9 & the end of treatment (month 2) to assess: 1) helpfulness of interventionist, 2) perceived clinical usefulness, 3) personal relevance, 4) level of engagement, and 5) overall satisfaction scored 1 (not at all) to 5 (extremely) on a Likert-scale. Data on acceptability of other aspects of intervention (e.g., group component, pre-quit NRT, nicotine patches, nicotine lozenges, and smoking text messages) will also be assessed using a 5-point Likert scale. Participants will also be asked to provide brief feedback on sessions after each session.

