Other measures of interest. Substance use. The timeline followback (TFB) method of assessment to collect data on use of marijuana and other substances. Other measures include: (Modified) Weight Bias Internalization Scale (WBIS), Internalized Stigma of Smoking Inventory (ISSI), Perceptions of Smoking-Related Stigma Scale (PSRSS), Brief Wisconsin Inventory of Smoking Dependence Motives (B-WISDM), Subjective Social Status Ladder (SSS Ladder), Everyday Discrimination Scale (EDS), Brief Self-Control Survey (BSCS), Paffenbarger (Physical Activity) Questionnaire, Self-Weighing Behavior, Eating Away from Home Questionnaire, Health Changes Questionnaire. Utilization of text-based support for quitting will be assessed by determining the number of participants who text “crave” or “slip” and the number of times an individual sends a message with either phrase.

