#### Data Analysis Plan

Feasibility & Acceptability. Average monthly number of individuals screened and enrolled will show feasibility of screening and recruitment. The proportion of participants completing the final study assessment will show feasibility of retention. Response to SR & LE conditions. Attendance. The percentage of treatment sessions attended through week 10 (one week post-quit) will be calculated and compared between conditions; average attendance of  $\geq$  70% in both arms suggests good acceptability. Participant Feedback. Participant ratings of intervention satisfaction mean scores  $\geq$  3.5 (5-point scale) shows acceptability in each condition.

Intervention effects on treatment outcome variables: Based on ITT principles, all assigned participants will be used in analyses regardless of adherence and missing data. Participants with missing data will be assumed to have smoked and to have regained 0.3 kg/month (positive imputation) and analyses will be repeated using multiple imputation for sensitivity analyses. Generalized estimating equations (GEE) Group x Time analyses will be used for weight change and abstinence. Abstinence. The dependent variable of 7-day point-prevalence abstinence will be analyzed by time (Quit Day, 1, 2, 3-months post-quit) and conditions. Weight. The dependent variable of weight, will be analyzed by time (baseline, Quit Day, 1, 2, 3- months post-quit) and conditions. Secondary exploratory analyses will repeat the GEE analyses adding sex as a variable, and (separately) adding any/no weight loss at week 9 as a variable in predicting smoking abstinence.

Putative mechanisms will be examined using regression analyses to test the effects of treatment on proposed mechanistic variables at week 9, controlling for baseline values. Regression analyses will also test the effects of these proposed mechanisms on follow-up smoking outcomes. Notably, detection of statistically significant effects is not an objective in this limited-powered study.

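### The two main outcome GEEs carry no baseline covariate, giving up a small amount of precision and some protection against chance imbalance that data already collected could supply

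*Combined protocol and SAP*

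**What the plan says.** The Data Analysis Plan sets one method for both outcomes: "Generalized estimating equations (GEE) Group x Time analyses will be used for weight change and abstinence". It then lists the terms. For abstinence, "The dependent variable of 7-day point-prevalence abstinence will be analyzed by time (Quit Day, 1, 2, 3-months post-quit) and conditions". For weight, "The dependent variable of weight, will be analyzed by time (baseline, Quit Day, 1, 2, 3- months post-quit) and conditions". No other variable appears in either main model.

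Two further sentences in that section matter:

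- The exploratory repeats add variables: "Secondary exploratory analyses will repeat the GEE analyses adding sex as a variable, and (separately) adding any/no weight loss at week 9". Sex is a baseline variable, but it enters only here. Week-9 weight loss is measured after allocation, so it cannot correct a baseline imbalance.
- The mechanism regressions are adjusted. They will "test the effects of treatment on proposed mechanistic variables at week 9, controlling for baseline values".

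Under Procedures, the baseline screening interview records "Age, number of cigarettes per day for past year, use other nicotine or tobacco products", and weight is measured at baseline. The B-WISDM dependence scale is listed among the other measures of interest, but the text available does not say when it is given. Groups of about 3-5 starters are randomised, not individuals, and no stratification is stated.

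**The concern.** Estimates of effect size for a larger trial are a stated product of this pilot. An estimate from 60 people can be moved by a chance difference between arms in how heavily people smoke, and nothing in the abstinence model offsets that. Cigarettes per day is a natural prognostic candidate. It also sets the patch schedule, so an imbalance in it brings an imbalance in nicotine dose. For weight, a Group x Time model with an unconstrained baseline mean in each arm amounts to a comparison of change scores, which is somewhat less precise than adjusting for baseline. The plan uses baseline adjustment for its mechanism question but not for the two outcomes named in its hypotheses.

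**Working it through.** The plan gives no SD, correlation, abstinence rate or power figure, so there is no stated figure to reproduce. From the documents: 60 participants, 30 per arm, groups of roughly 4-5. Everything marked *assumed* is not in the documents.

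**1. Chance imbalance**
- SE of a standardised baseline difference = √(2/30) = 0.258 SD.
- P(|difference| > 0.3 SD) = 2[1 − Φ(0.3/0.258)] = 24.5%, if individuals were randomised.
- With groups of size m, the SE is √((2/30) × DEFF), where DEFF = 1 + (m − 1) × ICC.
- *Assumed* ICC 0.05, m = 4: DEFF 1.15, SE 0.277, probability 27.9%.
- *Assumed* ICC 0.10, m = 5: DEFF 1.40, SE 0.306, probability 32.6%.

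**2. Weight**
*Assumed* SD 15-18 kg and change SD 4-6 kg, equal variances, complete data.
- Correlation ρ = 1 − (change SD)²/(2 × SD²).
- Lowest: 1 − 36/450 = 0.920. Highest: 1 − 16/648 = 0.975.
- Variance of the arm difference is proportional to 2(1 − ρ) for change and to 1 − ρ² with baseline adjustment. The ratio is (1 + ρ)/2.
- Ratio 0.960 to 0.988: a variance cut of 4.0% to 1.2%, or an SE cut of 2.0% to 0.6%.
- Effect of a 0.3 SD baseline imbalance on the change contrast = (1 − ρ) × 0.3 × SD. This is 0.08 × 4.5 = 0.36 kg at the lowest ρ and 0.025 × 5.4 = 0.13 kg at the highest.
- SE of the change contrast = change SD × 0.258 = 1.0 to 1.5 kg.

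**3. Abstinence: shift from an imbalance**
*Assumed* LE abstinence 20%, treatment OR 2.45, covariate OR 0.5-0.7 per SD.
- SR odds = 0.25 × 2.45 = 0.6125, so SR abstinence is 38%. The assumed difference is 18 points and the average rate is 0.29.
- Shift for a one-standard-error imbalance (0.258 covariate SD) ≈ |ln OR| × 0.258 × 0.29 × 0.71.
- OR 0.7: 0.357 × 0.258 × 0.206 = 1.9 points. OR 0.5: 0.693 × 0.258 × 0.206 = 3.7 points.
- SE of the risk difference = √(0.20 × 0.80/30 + 0.38 × 0.62/30) = 11.5 points, taking participants as independent.

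**4. Abstinence: precision**
- Simulation of 4,000 trials under these assumptions gave adjusted/unadjusted variance ratios of 0.99, 0.97 and 0.92 for covariate ORs of 0.7, 0.6 and 0.5 per SD.
- Hand check: the share of variance explained is about (ln OR)² × 0.206, which is 0.026 at OR 0.7 and 0.099 at OR 0.5, before the small cost of one more parameter.
- A repeated-measures GEE simulation (60 people, four visits, 400 runs per setting, about 1% of fits failing) gave ratios of 1.00 at a log odds ratio of 0.5 per SD and 0.96 at 0.8. Its coefficients are conditional on a person-level random effect, so the marginal association is weaker.
- Together these give a variance cut of about 0-8%.

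**The case against.** The case for leaving the models alone is a strong one.

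- **Validity.** Unadjusted comparisons are valid under randomisation. Chance imbalance is already part of the 11.5-point SE. A reader might infer that the planned estimates are biased; the documents do not support that.
- **Weight.** A reader might infer that a baseline weight difference passes straight into the weight result. It does not. Baseline is a time level, so the interaction compares change, and about 92-98% of any baseline difference is already removed.
- **Inconsistency.** The mechanisms are measured only at baseline and week 9, so regression on baseline is their natural form. Abstinence has no baseline value, because everyone smokes at entry. The contrast with the mechanism regressions is real but does not show an error.
- **Outcome wording.** The plan names weight change in one sentence and weight in the next. A reader might see two competing outcomes. A Group x Time test on weight is a test of change, so this is largely wording.
- **Purpose and size.** The plan disclaims significance testing, and the logistic model is already full: 2 arms × 4 visits = 8 mean parameters, with about 30 × 0.20 + 30 × 0.38 = 17 abstinent people per visit under the assumed rates.

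All of this limits the size of the point, and the first two items remove any claim of bias. What remains is that effect estimates are a product of this trial, and a disclaimer about significance does not make a steadier estimate worthless. One covariate named in advance also closes off a choice that could otherwise be made after the data are seen.

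**Conclusion.** The point holds as a minor improvement; no stated figure in the plan is wrong. The main outcome models omit baseline covariates that are already collected. The cost is about 1-4% of variance for weight and 0-8% for abstinence, plus exposure to a chance imbalance that would typically move the abstinence difference by 2-4 points against an SE of 11.5. These sizes rest on assumed SDs, abstinence rates, treatment effect and covariate strength. The 18-point difference used as a yardstick is likewise assumed, since the plan says only that it expects a medium effect. The argument is stronger for abstinence, where nothing offsets an imbalance, than for weight, where most of it is already removed. Allocation by small groups without stated stratification makes imbalance somewhat more likely than the simple 25%.

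**What to change.** Amend the Data Analysis Plan as follows.

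- **Abstinence.** Add baseline cigarettes per day as the single pre-specified covariate. Report a standardised risk difference beside the odds ratio. Do not substitute B-WISDM unless the assessment schedule confirms that it is measured at baseline.
- **Weight.** Model weight at Quit Day and at 1, 2 and 3 months, with baseline weight as a covariate. Alternatively, keep baseline as a time level with the two arm means constrained equal. Report within-arm change from baseline descriptively, since the SR programme has a pre-quit weight-loss goal.
- **Wording.** Use one name for the weight outcome throughout.

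The cost is wording only: no new data, visits or participants. There are two small downsides. The adjusted odds ratio is conditional on the covariate, which is why the standardised risk difference is needed, and one parameter is added to a small logistic model. The covariate should be fixed before outcome data are examined.

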### **Specific Aims**

We aim to conduct a small RCT with 60 OB smokers comparing SR to LE, with both conditions subsequently receiving smoking cessation counseling and combination nicotine replacement therapy to assess intervention feasibility and acceptability and obtain preliminary effect size data regarding the following hypotheses: Smokers in the SR vs. LE condition will have better biochemically verified point-prevalence abstinence from smoking at the end of smoking cessation treatment and at follow-ups, with a medium effect size. Smokers in the SR vs. LE condition will have less weight gain at the end of smoking cessation treatment and at follow-ups, with a medium effect size.

We will also examine potential mechanisms of action for efficacy of SR on improved smoking outcomes, expecting that: Smokers in the SR vs. LE condition will have greater increases in self-efficacy for managing weight and for quitting smoking and greater decreases in negative affect and delay discounting prior to quitting. Self-efficacy, negative affect, and delay discounting will be associated with abstinence at follow-ups.

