### **Methodology**

#### **Project Purpose**

This project focuses on collecting pilot data to inform a larger clinical trial for preventing weight gain and improving smoking cessation outcomes in overweight and obese smokers who are disproportionately at risk for disease, disability, and premature death but may be reluctant to give up smoking due to the fear of subsequent weight gain and trouble managing their weight without cigarettes. Helping these individuals lose weight prior to quitting smoking could provide a buffer against post-cessation weight gain and may improve mood, help increase the salience of future health outcomes, and increase self-efficacy for tackling the challenges associated with quitting smoking. Use of a multiple health behavior change intervention can maximize anticipated health benefits of smoking cessation and reduce the potential for relapse to smoking due to post-cessation weight gain. With an effective program, more overweight or obese smokers may be willing to attempt smoking cessation which could impact the two leading causes of preventable mortality in the US.

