Self-regulation plus large changes in behavior (SR). The active intervention is based on self-regulation theory and is similar to interventions tested previously and shown to be effective in reducing weight gain and weight regain. The initial 8-week program will include weekly group sessions focused on teaching self-regulation and efforts to produce a 10 lb weight loss to buffer against anticipated post-cessation weight gain based on the SR approach. The key concepts of the intervention: Self-Regulation. Participants will be taught the core self-regulation skills for controlling their weight: a) weighing themselves daily; b) detecting small changes in weight as soon as they occur; c) implementing problem-solving skills and learned strategies to combat changes in weight; d) evaluating the success of strategies implemented; e) rewarding themselves for successful weight loss and weight maintenance or f) making behavioral changes if weight gain occurs. These strategies are introduced over the course of the 8 weeks, with the initial weeks stressing the importance of daily self-weighing and learning to use the scale for information (rather than self-evaluation). At the end of the initial 8 weeks, the participants will be introduced to a color-coded system to help them accomplish steps b-f of the self-regulation model. The goal for the first 8 weeks of the program will be to lose 10 lbs in order to buffer against expected weight gain. To accomplish this, participants will be given a reduced calorie goal (1200-1500 kcal/day if <200 lbs or 1500-1800 kcal/day if >200 lbs). They will be instructed to self-monitor their intake and taught strategies for reducing caloric intake (e.g. reducing fat content of foods) and strategies for dealing with high-risk situations such as eating out. Structured physical activity, which is activity similar in intensity to brisk walking that lasts at least 10 minutes, will also be prescribed and self-monitored, starting with a goal of 50 minutes per week (10 minutes per day on 5 days per week) and gradually increasing to 150 minutes per week.

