Weeks 9-16 will focus on smoking cessation, but each session will include a private weigh-in and brief group discussion of strategies to maintain weight loss and prevent post-cessation weight gain. To maintain the weight losses achieved thus far and prevent post-cessation weight gain, participants will be taught to use a color zone system (Red, Yellow, Green) for weight maintenance to guide their behavior after completing the initial 8-week weight control program. The weight goals used to define the zones will be individually tailored based on the initial weight changes. Participants will be encouraged to weigh themselves daily and at the end of each week and to assess their current weight relative to their individual color zones. If participants are in Green, they will be encouraged to reinforce their success (with a sticker or small amount of money); if they are in Yellow they will be taught to begin monitoring their behavior more carefully and identify area to make changes to get back on track; if they are in Red, they will be encouraged to return to full self-monitoring of intake and activity and resume their original calorie intake and goals. During smoking cessation, the goal will be to minimize weight gain for those who achieved targeted weight loss as well as for those who did not. This Red, Yellow, Green system for weight maintenance has had demonstrable success in prior studies of the self-regulation model.

Healthy lifestyle education attention-placebo control (LE). Participants in this group will be provided with information on the obesity epidemic and the importance of a healthy lifestyle to use at their own pace as they wish. They will receive basic education about principles of healthy eating (e.g., simple vs. complex carbohydrates) and physical activity during the first 8 sessions. During sessions 9-16, the focus will be on smoking cessation. Sessions will also include lifestyle education information such as why weight gain occurs after smoking cessation. This group will not be taught any specific behavioral self-regulation skills to help them change their behaviors. Providing basic education about diet and exercise has produced minimal weight loss in other clinical trials.

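### Is the pilot's weight effect left undefined because the plan names no reference visit, no start for the imputed regain and no standardising SD?

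*Combined protocol and SAP*

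**What the plan says.** Specific Aims says the trial is to "obtain preliminary effect size data regarding the following hypotheses". The weight hypothesis is that SR will show "less weight gain at the end of smoking cessation treatment and at follow-ups, with a medium effect size" compared with LE.

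For the model, the Data Analysis Plan says GEE "Group x Time analyses will be used for weight change and abstinence". For weight it adds: "The dependent variable of weight, will be analyzed by time (baseline, Quit Day, 1, 2, 3- months post-quit) and conditions". For missing data it says: "Participants with missing data will be assumed to have smoked and to have regained 0.3 kg/month (positive imputation". The analyses are then to be repeated under multiple imputation as a sensitivity analysis. The same section says that statistical significance is not an objective.

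Two parts of the document bear on the reference point. Project Purpose gives the rationale: "Helping these individuals lose weight prior to quitting smoking could provide a buffer against post-cessation weight gain". The SR description under Procedures sets the pre-quit target: "The goal for the first 8 weeks of the program will be to lose 10 lbs in order to buffer against expected weight gain". For weeks 9-16 the same description says: "During smoking cessation, the goal will be to minimize weight gain". LE is expected to produce little weight loss.

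**The concern.** If significance is not sought, the estimate is itself a product of the pilot and will inform the larger trial. Three things that set it are not written down.

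- **Reference visit.** The buffer rationale suggests net change from baseline. The aim for weeks 9-16 suggests change from Quit Day. SR is designed to lose weight between those two visits and LE is not, so the two contrasts can differ in size and even in sign.
- **Start of the imputed regain.** Counted from the last observed weight, both arms receive the same increment, so a difference present at Quit Day is carried forward for everyone who then goes missing. Counted from baseline weight, that difference is erased for them.
- **Standardiser.** The outcome is called weight change in one sentence and weight in another. A given difference in kg is a much smaller standardised effect on the SD of body weight than on the SD of change.

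On this view, two analysts who both follow the plan could report effects of different size, or of opposite sign, from one dataset.

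**Working it through.** The plan gives no SD, correlation, dropout rate or numerical effect size, so it has no figure to reproduce.

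**Inputs from the documents.** SR goal 10 lb = 4.54 kg; imputed regain 0.3 kg/month; 8 weeks = 1.84 months before Quit Day; 30 per arm.

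**Assumed inputs.** SR-LE difference at Quit Day D = 2.27 kg (half the goal, LE unchanged); SD of change from baseline 4 kg; correlation 0.7 between changes at two visits; 10-30% of each arm missing after Quit Day.

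**1. One SR participant who met the goal and is then missing, as entered at month 2**

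| Regain counted from | Change from baseline | Change from Quit Day |
|---|---|---|
| Quit Day weight and date | -4.54 + 0.3 × 2 = -3.94 kg | +0.60 kg |
| Baseline weight, Quit Day date | +0.60 kg | 4.54 + 0.60 = +5.14 kg |
| Baseline weight and date | 0.3 × 3.84 = +1.15 kg | 4.54 + 1.15 = +5.69 kg |

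The spread for one person is wide, but the largest values need both a baseline start and a Quit Day reference.

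**2. Reference visit, no missing data**

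- Difference gone by month 2: 0 from baseline; +2.27 kg from Quit Day. The SD of change from Quit Day is 4 × √(2 × 0.3) = 3.10 kg, so d = 2.27/3.10 = 0.73 against SR.
- Difference kept: -2.27 kg from baseline, d = 2.27/4 = 0.57 for SR; 0 from Quit Day.

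In each case the two results are linear contrasts of the same arm-by-visit means. They answer two questions from one fit and do not conflict.

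**3. Start of the imputed regain, baseline contrast at month 2, missing fraction f equal in both arms**

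Moving the start from last weight to baseline weight changes the contrast by f × D: 0.1 × 2.27 = 0.23 kg to 0.3 × 2.27 = 0.68 kg.

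- Difference truly gone by month 2: a last-weight start gives -0.23 to -0.68 kg; a baseline start gives 0, which is correct.
- Difference truly kept: a last-weight start gives -2.27 kg, which is correct; a baseline start gives -2.27 × 0.9 = -2.04 kg to -2.27 × 0.7 = -1.59 kg.

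Neither start is better in both cases. With the full goal as D, the shift is 0.1 × 4.54 = 0.45 kg to 0.3 × 4.54 = 1.36 kg.

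For anyone missing from Quit Day onwards, the last observed weight is the baseline weight, so the two starting weights coincide.

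**4. Precision for comparison**

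The 95% half-width from baseline is 2.00 × 4 × √(2/30) = 2.1 kg; from Quit Day it is 2.00 × 3.10 × √(2/30) = 1.6 kg. Clustering by treatment group is ignored and would be expected to widen both.

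**5. Standardiser**

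2.27 kg is d = 2.27/5 = 0.45 to 2.27/3 = 0.76 on an assumed SD of change of 3-5 kg, and 2.27/20 = 0.11 to 2.27/15 = 0.15 on an assumed body-weight SD of 15-20 kg. The estimate in kg is the same throughout.

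**6. What the text says about the reference**

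Baseline is a time level for weight but not for abstinence. The exploratory analysis uses any or no weight loss at week 9, which can only mean loss since baseline. Potential Risks and the risk-minimisation procedures both measure weight loss from baseline. The plan invokes intention-to-treat, and baseline is the only listed weight taken before assignment. The one passage that favours Quit Day describes the coaching goal for SR participants and does not define an outcome.

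**The case for a change.** The strongest opposing case is that low power excuses an imprecise estimate but not an undefined one. A Group x Time term over five visits is not a single effect size. The hypothesis speaks of weight gain around cessation, which can be read as gain after Quit Day. The word for regaining weight does not fit an LE participant who lost none. A last-weight start builds into the main analysis, for missing people, the lasting buffer that the hypothesis is meant to examine. Multiple imputation is only a sensitivity analysis and settles neither the reference visit nor the SD. Writing the definitions down would be cheap.

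Much of this is literally true: the plan names no contrast, no start and no SD. What does not stand is the step from there to an unreliable result. The reference visit and the SD affect only how one set of fitted means is summarised, and either contrast remains available to whoever plans the larger trial. The carry-forward worry is real, but it has a mirror image: a baseline start would assume the buffer away. At D = 2.27 kg the choice moves the estimate by at most a third of its half-width (0.68/2.1 = 0.32). Multiple imputation does not use the 0.3 kg rule, so it would reveal any dependence on it.

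**Conclusion.** The concern identifies missing detail, not a faulty analysis. A competent analyst following the plan would report the SR-LE difference in change from baseline by visit, count the regain from the last observed weight, and set the planned multiple imputation beside it. That result would be sound.

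The one choice that alters the data moves the baseline contrast by 0.23-0.68 kg under the main assumptions. If the full 10 lb difference is reached and 30% are missing, it moves it by 1.36 kg. Both lie inside a half-width of about 2.1 kg, and which start is nearer the truth depends on whether the Quit Day difference persists. The reversed-sign result requires a Quit Day reference, which the documents support less well, and even then it is a second contrast from the same fit. The standardiser is a matter of reporting.

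These sizes rest on an assumed D, SD, correlation and missing rate, none of which the documents give. The reading of the text in favour of baseline does not depend on them. No change to the plan is called for.
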